4.4.4.3 Tipping Point Sensitivity Analysis

In addition to the above methods for handling missing data, if the treatment effect on the primary analysis is significant, a 'tipping point' sensitivity analysis of the primary outcome will be performed. This analysis assesses the impact of missingness across a continuum of assumptions until the 'tipping point' is identified. This is the point at which the assumption regarding the effect of the treatment in subjects with missing data nullifies or reverses the treatment effect obtained in the primary analysis. Implementation of this sensitivity analysis mimics standard multiple imputation and is described below:

1. For any Class 1 missing 4SC values, use the mean and SD of all non-missing values for the respective treatment group to generate the imputed values from a normal distribution. Note that any Class 2 missing 4SC values should continue to be imputed with twice the maximum non-missing value recorded across all subjects as applicable per the above rules.
2. Implement Step 1 10 times so that 10 complete datasets are produced. For each of these datasets, find the change from baseline to 18 months in 4SC values for each subject.
3. Analyse the 10 complete datasets; this should be performed as described in Section 4.4.2 using the PROC MIXED approach described in Section 4.4.4.2.
4. Combine the results from the 10 data sets using Rubin's methods via PROC MIANALYZE for inference.
5. Repeat Steps 1 to 4 but now with an appropriate small shift ($+\delta$) applied to the individual subject values for the change from baseline in 4SC in the givinostat treatment group (but not to the placebo group). This shift is applied after step 2, i.e. after the generation of the datasets including any imputation, and after finding the change from baseline values but prior to the analysis of these. The directionality of the shift will be such that this reduces the treatment difference between givinostat and placebo.
6. Display the estimated treatment effect and associated 2-sided CIs vs degree of shift.
7. Repeat Steps 5 and 6, increasing the shift each time as $+2\delta$, $+3\delta$, ..., $+(\text{treatment effect seen in the primary analysis})$.
8. Identify the tipping point where $p > 0.025$.

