4.4 Statistical Analysis

4.4.1 Hypothesis to be Tested

The null hypothesis being tested for the primary endpoint is that there is no difference in mean change in 4SC from baseline to 18 months between the givinostat and placebo treatment groups:

$$H_0: 4SC_{givinostat} = 4SC_{placebo}$$

The alternative hypothesis is that there is a difference in either direction in the mean change in 4SC from baseline to 18 months between the givinostat and placebo treatment groups:

$$H_0: 4SC_{givinostat} \neq 4SC_{placebo}$$

All tests will be two directional and thus references to 1-sided p-values throughout this SAP refer to significance in either direction. For all analyses, 2-sided p-values will be presented and will be subject to the relevant significance level in either direction, as stated in Section 4.4.5. Similarly, 2-sided CIs will be presented.

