The time to event variables (time to 10% persistent worsening in 6MWT, time to persistent loss of standing) will be analysed using Cox proportional hazards modelling, including baseline values for: 4SC, time to rise from floor, time to run/walk 10 metres, distance walked in 6 minutes and re-derived age at first dose (in years and months) as independent covariates and randomised treatment group and concomitant steroid

use as independent classification factors. The hazard ratio will be presented, together with its associated 2-sided CI and p-value.

Where adjustment of alpha is applied to any of the above analyses per the methods described in Section 4.4.5, the 2-sided CIs will be subject to the corresponding adjustment. Thus the adjusted 2-sided CIs will be as indicated in the following table:

Analysis Time Point	Endpoint	Applicable p-value (1-sided)	Applicable p-value (2-sided)	CI (2-sided)
Final analysis	4SC at 18 months in the target population	$p \leq 0.025$	$p \leq 0.05$	95%
Final analysis	Key secondary efficacy endpoints at 18 months in the target population	$p \leq 0.025/i$ (i = rank according to Hochberg procedure)	$p \leq 0.05/i$ (i = rank according to Hochberg procedure)	$100(1-0.05/i)\%$ (i = rank according to Hochberg procedure)
General	All other analysis (supportive only)	$p \leq 0.025$ (nominal p-values presented)	$p \leq 0.05$ (nominal p-values presented)	95%

For the final analysis of key secondary efficacy endpoints at 18 months in the target population, unadjusted 95% CIs will be presented in the individual analysis tables. However, the applicable adjusted CIs following the Hochberg procedure will be given in an overall summary of these endpoints per Section 4.4.5.

Further, as a reflection of the overall totality of evidence for a treatment effect on functional outcomes, the primary endpoint and the functional key secondary endpoints (as detailed in Section 4.2.1) will be subject to assessment by Hochberg. This is equivalent to considering the primary and functional key secondary endpoints as equally important facets of the disease such that an improvement in any one, or more than one, of these endpoints can be considered to reflect a clinically meaningful benefit to the patient.

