4.4.4 Handling of Missing Data

4.4.4.1 Classification and Imputation

For the efficacy analyses, any missing data for continuous values for a subject will be classified as follows:

1. the subject has missing data due to reasons other than being non-ambulatory or physically unable to perform the test / assessment
2. the subject has missing data due to being either non-ambulatory or otherwise physically unable to perform the test / assessment.

Any missing values classified as 1 will be imputed using the mean of all non-missing values for the respective measurement and timepoint across all subjects randomised to the respective treatment and in the respective concomitant steroid stratum and Group (i.e. Group A, target population or Group B, off-target population).

Any missing values classified as 2 will be imputed by setting the value to zero or to twice the maximum non-missing value recorded across all subjects depending on the directionality of the test.

In all cases, imputation of any data classified as 1 will be completed first, followed by imputation of any data classified as 2.

Classification and imputation of missing data will be completed prior to any transformation of the data for analysis. For example transformation of the timed function test results for presentation of velocity or any log transformation applied as needed (per Section 4.4.2).

For binary or time to event variables where missing data means that the binary response or time to event cannot be determined, the missing data from which the variable is derived (e.g. 6MWT values) will first be classified and imputed, as described above, in order to then derive the binary response or the time to event. Exceptions to this are where the criteria for deriving the binary response themselves refer to presence of missing data, for example loss of ambulation. The classification described above will be used for the relevant missing data in these cases in order to confirm physical inability to complete the respective test. Further details are given below regarding the rules for derivation of the binary endpoints in the presence of missing data.

For the NSAA assessment, where the total score is a sum of ordinal item scores, imputation of Class 1 and Class 2 data will follow a different approach as defined in Appendix 7.5.4.

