4.4.5 Adjustment for Multiple Comparisons

The p-value applicable to the final analysis of 4SC at 18 months in the target population will be $p \leq 0.025$ 1-sided. For final analysis of the key secondary efficacy endpoints at 18 months in the target population, adjustment for multiple comparisons will be applied as described below. For all other analyses (i.e. for different endpoints or timepoints in the target population, or analyses in the overall population), analysis will be considered supportive only. Therefore, nominal p-values will be presented and the significance level applicable will be $p \leq 0.025$ 1-sided.

In accordance with EMA (European Medicines Agency, 2002) and FDA guidelines (U.S. Food and Drug Administration, 2017), the assessment of multiple key secondary efficacy endpoints at 18 months in the target population at the final analysis will be accounted for using the Hochberg procedure (Hochberg, 1988).

The key secondary efficacy endpoints are given in [Section 4.2](#) (time to rise from the floor, 6MWT, muscle strength evaluated by knee extension, muscle strength evaluated by elbow flexion, physical function as measured by total NSAA score, physical function as measured by cumulative loss of function on the NSAA, VL MFF as assessed by MRS). Each of these endpoints will be analysed and the resulting 1-sided p-values will be ordered in descending order, from least to most significant. The highest p-value will then be compared with 0.025, the specified level of significance for the primary endpoint at the final analysis for this study, and if it is >0.025 , the subsequent p-value will be considered in relation to $0.025/2=0.0125$. As

soon as the i th endpoint has a corresponding p-value $< 0.025/i$, the treatment effects for that endpoint and all of the endpoints following it are considered to be significant. A table will be presented summarising the p-values and associated adjusted 2-sided CIs from each of the key secondary efficacy endpoints with significance indicated according to the above approach.

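### SAP 4.4.4.3 gives its tipping threshold of 0.025 no side, imputes missing 4SC times from the arm mean and SD alone, and does not limit the shift to imputed values

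*SAP*

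**What the plan says.** SAP 4.4.4.3 runs if the primary 4SC result is significant. Its steps relevant here are:

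- **Step 1.** Class 1 gaps in 4SC are filled by this rule: "use the mean and SD of all non-missing values for the respective treatment group to generate the imputed values from a normal distribution". Steps 2–4 do this 10 times, analyse each dataset with the PROC MIXED model and combine the results by Rubin's rules.
- **Step 5.** A shift that shrinks the treatment difference is added to the change values of givinostat subjects, after imputation and not to placebo. The text does not confine it to subjects whose value was imputed.
- **Step 6.** "Display the estimated treatment effect and associated 2-sided CIs vs degree of shift".
- **Step 7.** The shift is increased up to the full treatment effect seen in the primary analysis.
- **Step 8.** "Identify the tipping point where" p is above 0.025. No side is given.

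Elsewhere, SAP 4.4.1 says: "For all analyses, 2-sided p-values will be presented and will be subject to the relevant significance level in either direction". SAP 4.4.4.2 takes the 2-sided CI and p-value from the LSmeans output. SAP 4.4.5 says: "The p-value applicable to the final analysis of 4SC at 18 months in the target population will be $p \leq 0.025$ 1-sided". The table in SAP 4.4.2 pairs 1-sided 0.025 with 2-sided 0.05 and a 95% CI, for 4SC and for supportive analyses. The primary Class 1 imputation (SAP 4.4.4.1) is finer than step 1: it averages values at the same timepoint over subjects "randomised to the respective treatment and in the respective concomitant steroid stratum and Group". SAP Addendum 1 does not amend 4.4.4.3.

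**The concern.** SAP 2.9 gives this analysis the task of assessing what missing data do to the primary result, and no other planned analysis varies the missing-data assumption for it. The primary analysis fills Class 1 gaps with a single mean, so the check matters.

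Three features weaken it.

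- **Threshold.** The p-value that reaches step 8 comes from the PROC MIXED route and is 2-sided under 4.4.1. A programmer who compares it directly with 0.025 applies a test twice as strict as the primary one. The output could then say tipped beside a 95% CI that excludes zero.
- **Draw.** An absolute climb time is drawn without regard to the boy's own baseline, and that baseline is then subtracted. The ANCOVA adjusts for baseline 4SC, age, steroid stratum and other functional baselines, and 4SC is measured at months 3 to 15. Step 1 uses none of this. The mean and SD are held fixed across the 10 datasets, and a normal draw can give a negative time.
- **Shift.** If every givinostat change value moves together, the tipping shift is close to the effect minus a multiple of its SE. That is not a statement about boys with missing data.

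**Working it through.** **Inputs.** Effect 2 s, 90% power, 1-sided 0.025, 2:1 allocation, N=102 (68/34) and 8% drop-out, from SAP 2.5. The SD of 3.094 s is called within-treatment in SAP 2.5 and Protocol 13.2, but overall in the interim account of the protocol synopsis.

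**Reproducing the plan's figures.** Placebo n = (1.960 + 1.282)² × SD² × 1.5 / effect².

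- Effect 3, SD 6: 64, so N=192, as stated.
- Effect 2, SD 3.094: 38, so N=114, not 102.
- Effect 2, SD √(3.094² − 1²) = 2.928: 34, so N=102, as stated.

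Both SDs are therefore carried below.

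**Threshold.** The normal quantile is 1.960 for 1-sided 0.025 and for 2-sided 0.05, so the SAP's pairing is exact. For 2-sided 0.025 it is 2.241. Because step 5 moves the givinostat values as a group, tipping shift = effect − z × SE, with SE = SD × √(1/68 + 1/34). This uses a normal approximation and no covariate gain.

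| SD (s) | SE (s) | Effect (s) | Tip at 2-sided 0.05 | Tip at 2-sided 0.025 |
|---|---|---|---|---|
| 2.928 | 0.615 | 2.0 | 0.795 | 0.622 |
| 2.928 | 0.615 | 1.5 | 0.295 | 0.122 |
| 3.094 | 0.650 | 2.0 | 0.726 | 0.543 |
| 3.094 | 0.650 | 1.5 | 0.226 | 0.043 |

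The gap is (2.241 − 1.960) × SE, or 0.173 s and 0.183 s. At 2 s that is 0.173/0.795 = 22% and 0.183/0.726 = 25%. The SD formula with its stated treatment effect of 3 s gives SD 2.706 s, SE 0.568 s and 0.726 s against 0.886 s, 18% early. With an observed effect of 1.25 s and SE 0.615 s, the 2-sided p is 0.042. The primary test succeeds, but 1.25 − 2.241 × 0.615 = −0.128, so the 2-sided 0.025 rule is already met at zero shift.

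**Step 1 draw.** This was simulated with 1,000 trials per setting, 73:37 boys, 10 imputations, Rubin's rules and baseline-adjusted ANCOVA. Assumptions not in the documents: baseline SD 1.5 s, change SD 3 s, data missing completely at random, and the correlations shown. The comparator draws from a model with treatment and baseline, with parameter draws. Tipping shifts at 2-sided 0.05:

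| Missing | Correlation | Step 1 (s) | Conditional (s) | Gap (s) |
|---|---|---|---|---|
| 8% | 0 | 0.747 | 0.775 | 0.03 |
| 8% | 0.4 | 0.778 | 0.891 | 0.11 |
| 8% | 0.6 | 0.808 | 0.995 | 0.19 |
| 15% | 0 | 0.651 | 0.687 | 0.04 |
| 15% | 0.4 | 0.606 | 0.779 | 0.17 |
| 15% | 0.6 | 0.657 | 0.957 | 0.30 |

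The mean estimate stays near −2 s throughout, so the loss is in the SE. The probability of a negative draw is Φ(−mean/SD): 2% for an assumed 4/2 s and 11% for 5/4 s.

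**Step 5.** With a share m of givinostat values imputed, shifting only those moves the arm mean by m × shift. Taking m = 0.08 from the drop-out rate, a 0.795 s move needs 0.795/0.08 = 9.9 s on the imputed values. Under step 7's limit (2 s in this example), the arm mean would move only 0.08 × 2 = 0.16 s.

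**The case against.** The strongest reply is that 0.025 is this SAP's 1-sided level throughout. SAP 4.4.5 labels it so, and its Hochberg text then compares 1-sided p-values with 0.025 without repeating the label. On that reading step 8 matches the primary test and the threshold error is zero. This stands: the defect is an unstated side that clashes with 4.4.1, not a proven wrong rule.

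A reader might also infer that the procedure stops at p > 0.025. It does not. Step 7 carries the shift on to the full effect and step 6 shows a 2-sided CI at each shift, so the point where the 95% CI reaches zero can be read from the planned output.

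A reader might infer that step 1 pools visits or includes Group B. The wording leaves this open, but step 2 concerns the change to 18 months and SAP 2.8 and 4.4.2 restrict efficacy analyses to the target population, so both limits are largely implied.

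Some step 1 faults are small. Omitting parameter draws understates the arm-mean variance by roughly 0.08² = 0.6% at 8% missing. Negative times would number fewer than one per dataset, since 11% of about 9 missing boys is just under one. The SAP says only that the method imitates multiple imputation. The simulated gaps rest on assumed correlations and missingness.

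Finally, the analysis is supportive and follows a significant primary result. That limits the consequence but does not make the output informative.

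**Conclusion.** The point holds in a limited form. Step 8 needs its side stated. On the 2-sided reading at a 2 s effect it reports tipping 0.17–0.18 s early (22–25%, for SD 2.928 or 3.094 s), and a primary result with 2-sided p between 0.025 and 0.05 could be called tipped at zero shift. On the 1-sided reading there is no error. Step 1 discards baseline and earlier-visit data. Under the simulation's assumptions this moves tipping about 0.03–0.19 s earlier at 8% missing; the gain from using earlier visits was not quantified.

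In the settings examined both effects make the result look less robust than it is. It would be wrong to infer that the primary test or its type I error is at risk: neither step enters it. The larger weakness in meaning is step 5, because a shift not limited to imputed values does not test the assumption about boys with missing data that the section sets out to test.

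**What to change.** - **Step 8:** write 2-sided p > 0.05 (1-sided p > 0.025), that is, the smallest shift at which the 2-sided 95% CI includes zero.
- **Step 1:** impute Class 1 values by arm, in the target population, from a model with baseline 4SC, the other SAP 4.4.2 covariates and all observed 4SC visits. Draw the model parameters afresh for each dataset and keep times positive, for example with PROC MI on the log scale.
- **Step 5:** apply the shift only to imputed Class 1 givinostat values, and extend the range in step 7 as needed, since the present upper limit may be too small to reach a tipping point.

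Steps 1 and 8 alone are not enough: without the change to step 5, the tipping shift stays near the effect minus 1.96 × SE. The cost is SAP wording and a standard PROC MI call, with no new data.

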2.9 COVID-19

It is noted that particular attention may need to be given to the impact on key efficacy or safety assessments as a result of the COVID-19 pandemic. Consideration of the different areas of impact has been made as described below.

Protocol deviations related to COVID-19 will be recorded under separate categories indicating the type of deviation and that this was due to COVID-19. The assigned categories will be presented in the protocol deviation listing and table summary of major deviations as described in [Section 3.2](#).

Subjects who prematurely discontinue the study due to COVID-19 will record this as their reason for withdrawal and this will be included in the summary of reasons for withdrawal as described in [Section 3.1](#).

Subjects with a modification, interruption or who permanently stop IMP due to COVID-19 will record this as the reason for modification and this will be presented in the summary and listing of IMP modifications as described in [Section 3.5](#).

Missing efficacy data will be subject to the imputation and analysis methods described in [Sections 4.4.4.1](#) and [4.4.4.2](#). Missing data due to COVID-19 will be assumed to be Class 1 missing data (due to reasons other than being non-ambulatory or physically unable to perform the test / assessment) and handled accordingly. The tipping point analysis described in [Section 4.4.4.3](#) will assess the impact of the missing data on the primary analysis.

In order to provide supportive information for interpretation of the key efficacy and safety analyses, a summary of the number and percentage of subjects with missing assessments at each scheduled visit will be presented by treatment group and overall for the following selected data on the ITT analysis set in the target population (efficacy data) or safety analysis set in the overall population (safety data) as appropriate:

- All primary and key secondary efficacy assessments

- Clinical laboratory
- Vital signs
- Electrocardiogram
- Echocardiography
- Pulmonary function test

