The need for a possible log transformation of these variables will be investigated prior to unblinding by assessing the ANCOVA model residuals without a treatment term. Where data are transformed for analysis, back transformation will be applied for the presentation of results. Presentation of the tables will be amended as needed for this, for example with the addition of an explanatory footnote.

Analysis of cumulative loss of function on the NSAA over 18 months of treatment with givinostat or placebo will be performed using negative binomial regression. The dependent variable will be the subject cumulative number of failures across all post-baseline visits. Total failed items at baseline, baseline values for: 4SC, time to rise from floor, time to run/walk 10 metres, distance walked in 6 minutes and re-derived age at first dose (in years and months) will be included as independent covariates in the model, with randomised treatment group and concomitant steroid use included as independent classification factors. The estimated cumulative number of failures across 18 months and associated 2-sided CIs from the model will be presented for each treatment group. The treatment effect will be presented as the ratio of cumulative failures for givinostat relative to placebo along with the associated 2-sided CI and p-value, where a lower ratio indicates a greater reduction in cumulative number of failures across 18 months for givinostat compared with placebo.

The binary efficacy variables (proportion of subjects with $\geq 10\%$ persistent worsening in 6MWT, proportion of subjects losing ambulation during the study) will be analysed using logistic regression. In each instance baseline values for: 4SC, time to rise from floor, time to run/walk 10 metres, distance walked in 6 minutes and re-derived age at first dose (in years and months), will be included as independent covariates. Randomised treatment group and concomitant steroid use will be included as independent classification factors. The odds ratio comparing the treatment groups will be presented, together with its associated 2-sided CI and p-value.

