Class 2: $x_{ijk} = 2 \times \text{Max}(x)$ where $\text{Max}(x)$ is the maximum non-missing value recorded for the variable across all subjects, regardless of treatment, stratum or Group.

Following the assignment of imputed values, the data x_{ijk} will be analysed as described in Section 4.4.2 and Sections 4.1 to 4.3.10, as relevant to the respective variable using PROC MIXED, ensuring that reference levels are stated for all class variables so that difference in LSmeans is calculated as givinostat-placebo. F-tests from PROC MIXED will be based on Kenward-Roger's adjusted degrees of freedom.

LSmeans for drug and placebo from this model, denoted \bar{x}_D and \bar{x}_P respectively, the difference in the LSmeans, $\bar{x}_D - \bar{x}_P$, and the associated 2-sided CI and p-value will be taken from the LSmeans statement in PROC MIXED.

Note that for the analysis of these variables on the transformed scale representing velocity rather than time, transformation will be applied to the imputed data x_{ijk} to give the velocity values u_{ijk} used in the analysis model described above. The results from the model will be presented on the transformed scale without back transformation and will be interpreted as estimates of velocity.

Variables with any Class 2 missing data where lower values are worse

For the following variables, the directionality is such that lower values represent a worse outcome:

- 6MWT
- Percent predicted 6MWT
- NSAA
- Muscle strength evaluated by knee extension and elbow flexion as measured by HHM.

If any Class 2 missing data are identified for these variables, the analysis of the variable will be performed as follows:

If x_{ijk} represents the value of the variable to be analysed for subject i randomised to treatment j at time k , then subjects with missing data will be imputed as

Class 1: $x_{ijk} = \bar{x}_{jk}$ where \bar{x}_{jk} is the mean of all non-missing values for the respective measurement at time k across all subjects randomised to treatment j and in the respective concomitant steroid stratum and Group (i.e. Group A, target population or Group B, off-target population).

Class 2: $x_{ijk} = 0$

The exception to this is the NSAA total score which will be derived from imputed item scores as described in Appendix 7.5.4.

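### The tipping-point shift in SAP 4.4.4.3 step 5 is not limited to imputed values; applied to the whole givinostat arm, it does not test the missing-data assumption

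*SAP*

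**What the plan says.** SAP 4.4.4.3 plans a tipping-point analysis of the primary endpoint, run only if the primary result is significant. It defines the tip as the point at which "the assumption regarding the effect of the treatment in subjects with missing data nullifies or reverses the treatment effect" found in the primary analysis.

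- **Step 1** draws Class 1 missing 4SC values from a normal distribution with the arm's observed mean and SD, while "any Class 2 missing 4SC values should continue to be imputed with twice the maximum non-missing value recorded across all subjects".
- **Steps 2–4** build ten completed datasets, derive the change from baseline, fit the ANCOVA to each and pool by Rubin's rules.
- **Step 5** repeats this with a shift "applied to the individual subject values for the change from baseline in 4SC in the givinostat treatment group (but not to the placebo group". On timing it says: "This shift is applied after step 2, i.e. after the generation of the datasets including any imputation".
- **Step 7** reads "Repeat Steps 5 and 6, increasing the shift each time as" successive multiples of δ, and ends at the treatment effect of the primary analysis.
- **Step 8** looks for p above 0.025.

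SAP 2.9 treats values missing because of COVID-19 as Class 1 and says that this analysis "will assess the impact of the missing data on the primary analysis". The SAP addendum does not touch the section.

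**The concern.** The stated purpose and step 5 do not agree. The purpose concerns boys whose outcome was not seen. Step 5 exempts only the placebo arm, so its wording takes in observed givinostat values and Class 2 values as well as imputed ones. If every givinostat boy is shifted by the same amount, the gap between observed and missing boys never changes, and that gap is the assumption under test.

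SAP 2.9 plans little else on missing values: it tabulates missing assessments by visit and arm and leaves further analyses post hoc. Its planned repeat analyses deal with visits outside the window. The primary analysis replaces each Class 1 value with a mean for the arm, steroid stratum and Group, so a working stress test of that choice is needed. A reader told that the result tips at under one second would take it as fragile to missing data, although the figure does not say how poor the unseen outcomes would have to be.

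**Working it through.** **Inputs.** From SAP 2.5: difference 2 s (originally 3 s), 90% power, 1-sided alpha 0.025, 2:1 allocation, N = 102, 8% drop-out, 110 randomised (about 73 v 37). The SD of 3.094 s is called within-treatment in SAP 2.5 and overall in the Protocol synopsis. The documents do not give the number of missing values, so it is varied here.

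**Planning figure.** Placebo n = (1.96 + 1.2816)² × SD² × 1.5 / 2².
- With 3.094 s as the overall SD and Δ = 2, the within-arm SD is √(3.094² − 1) = 2.93 s. Then n = 33.8, rounded up to 34, total 102: the plan's figure.
- With 3.094 s as the within-arm SD, n = 37.7, rounded up to 38, total 114.

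Both SDs are carried forward; results that differ are shown as ranges.

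**Algebra, untransformed scale.** Adding δ to every givinostat change adds δ times the treatment column of the design matrix. The treatment coefficient therefore rises by exactly δ. Residuals do not change, nor does the standard error within each dataset. All ten estimates move together, so the between-imputation variance does not change either. The tip is the distance from zero to the nearer confidence limit of the unshifted pooled estimate, whatever is missing.

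**At planning values.** SE = 3.094 × √(1/37 + 1/73) = 0.624 s. The whole-arm tip is 2 − 1.96 × 0.624 = 0.78 s. At the last step 7 point (δ = 2) the difference is exactly zero.

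If only a fraction f of givinostat values is shifted and the SE is held fixed, the difference moves by about fδ. With f = 8%, the tip is 0.776 / 0.08 = 9.7 s, and at δ = 2 the difference is still −2 + 0.08 × 2 = −1.84 s.

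**Simulation of steps 1–8.** 500 trials per setting, 73 v 37, ten imputations, Rubin's rules with small-sample degrees of freedom, 2-sided 0.05. The ANCOVA had treatment and baseline only. Assumed: baseline mean 3.5 s, SD 1.3 s, correlation of change with baseline 0.3, all missing values Class 1. Trials were kept if both the primary and the unshifted pooled analyses were significant. Median tips for a true effect of −2 s:

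| Givinostat values missing | Whole-arm shift (s) | Imputed values only (s) |
|---|---|---|
| 0/73 | 0.91–0.92 | none exists |
| 2/73 | 0.84–0.86 | 18.5–18.7 |
| 6/73 | 0.83 | 7.9 |
| 11/73 | 0.73–0.88 | 4.3–5.0 |
| 18/73 | 0.68–0.70 | 2.6–2.7 |

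- At 6/73 the interquartile ranges are 0.48–1.28 s and 4.9–11.1 s.
- With a true effect of −3 s and 6/73 missing, the medians are 1.67–1.75 s and 14.0–14.3 s.
- At 6/73 the imputed-only tip lies beyond the step 7 end point in 95–96% of trials (−2 s) and in all of them (−3 s).
- With the two worst boys per arm set to the Class 2 value, the 6/73 figures are 0.70–0.73 s and 7.2–7.5 s.
- In every trial the whole-arm tip matched the confidence-limit distance to within rounding error.

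**Log scale.** SAP 4.4.2 states: "The need for a possible log transformation of these variables will be investigated prior to unblinding". If a log transformation were used, a shift in seconds would lose the exact identity. With lognormal values, nothing missing, a mean difference of −2.4 s and an SD of change of 3.1 s, the SE changed by a median of −13%. A whole-arm shift still produced a tip, at a median of 0.93 s.

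**The case against.** Step 5 does not say that all values are shifted, and the opening of the section points to boys with missing data. The two apparent clues to a whole-arm shift are weak. Change scores exist only after imputation, so the timing sentence fits either reading. The step 7 end point also suits an imputed-only shift: adding the whole treatment effect to values drawn from the givinostat mean puts missing boys at about the placebo level, a natural stopping place. On that view one qualifier in step 5 would do, and the existing grid asks a fair question: does significance survive if missing givinostat boys had no benefit?

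Much of this is right. The clues do not prove intent, and survival to zero benefit is a reportable result. But step 1 names Class 1 explicitly and step 5 names no class, so a programmer following the text would shift the arm. The section also sets out to increase the shift until a tip is found, which the existing grid would seldom do under an imputed-only shift at 6/73.

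It is also fair that the error is conservative and confined to a supportive analysis, that the unshifted steps 1–4 are themselves a useful check on mean imputation, and that the two tips are on different scales: 0.83 s across 73 boys is about 61 s in total, 7.9 s across 6 is about 47 s. That difference of scale is why the whole-arm figure cannot be read as tolerance to missing data.

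**Conclusion.** The concern holds. As written, step 5 does not carry out the purpose stated for the section, and no other passage corrects it. Under the whole-arm reading on the untransformed scale, the reported tip restates the confidence-limit margin. That result is algebraic and needs no assumption about missingness.

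The gap between the two tips does depend on assumed inputs: about tenfold at 6/73 missing and about fourfold at 18/73, for a true effect of −2 s. The simulation model omits the steroid strata, age and the other baseline functional covariates. In every setting computed, the whole-arm tip was the smaller, so the bias is towards understating robustness to missing data. It cannot create a false efficacy claim. The section should be corrected, but the primary conclusion does not depend on it.

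**What to change.** - **Step 5:** add δ only to the imputed Class 1 18-month values of givinostat boys. Leave observed values, Class 2 values and all placebo values as they are.
- **Step 7:** continue the grid beyond the primary effect to a limit stated in advance. One candidate is that no shifted 18-month value may be worse than the Class 2 value, twice what SAP 4.4.4.2 says "is the maximum non-missing value recorded for the variable across all subjects, regardless of treatment, stratum or Group". Because a single off-target boy could set that maximum, a fixed limit in seconds chosen while blinded would also serve. Keep the zero-benefit point as a named row in the output.
- **Reporting:** state *not tipped within range* if significance holds up to the limit or if no givinostat value was imputed. With the Class 2 limit (median 16–17 s at 6/73 in the simulations), this occurred at −2 s in 3–4% of trials at 6/73 and 48–55% at 2/73, and at −3 s in 30–34% at 6/73.
- **Step 8:** for clarity only, label the threshold as 1-sided p > 0.025 (2-sided p > 0.05), in line with the table in SAP 4.4.2.

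The cost is the wording of steps 5 and 7, a label in step 8 and a small programming change. No new data are needed. Steps 5 and 7 should change together.
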